5.2 Exclusion criteria for enrollment

Outcome measurements will be confined to those who meet the trial inclusion criteria (AD diagnosis, no physical co-morbidities that preclude participation in the daily group intervention).

6.0 STATISTICS

All analyses will include factors for facility and intervention (nested within facility). Baseline analyses will include descriptors of the study sample (age, gender, ethnicity, onset of Alzheimer's disease) as well as initial levels of the outcome measures (depression, cognition, behavior) and will utilize analysis of variance for continuous data and chi-square methods for categorical data to compare the intervention groups. If the intervention groups are found to differ on baseline levels of the outcome variables or other variables related to outcome, these variables will be included as adjusting covariates in the comparisons of 12-week outcomes. 12-week outcomes will be compared between intervention groups with analysis of variance (2-level factor for intervention, 8-level factor for facility, with intervention nested within facility). For planning of larger trials, the following estimates will be made (along with 95% confidence intervals) for each patient outcome: intervention effect size (mean group difference in outcome), variance in outcome (across patients, across facilities), within-facility correlation in outcomes (correlations in outcomes amongst patients within a facility), within-patient correlation in outcomes (repeated measures, baseline and 12-weeks).

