4.0 TREATMENT OF SUBJECTS

4.1 Intervention Group

At two facilities, the active light intervention will enlist staff to increase daylight exposure to Alzheimer residents by taking them to daylit perimeter room in the morning (8:00 - 10:00 AM) where vertical daylight illuminance at eye level exceeds 2500 lux and where direct sun exposure

can be avoided. The intervention will consist of two hours of daylight exposure administered beginning at 8:00 AM in the morning each day (7 days / week) over the 12-week study.

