4.2 Control Group

Patients at the other two facilities will receive usual care. During the period from 8:00 AM to 10:00 AM each day, the control group of Alzheimer residents will be taken to a similar sized area indoors without daylight exposure for socialization under typical interior fluorescent lighting conditions.

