5.0 SELECTION AND EXCLUSION OF SUBJECTS

5.1 Inclusion criteria for enrollment

The trial inclusion criteria is an AD diagnosis and no physical co-morbidities that preclude participation in the daily group intervention. Based on current facility records, we estimate the intervention and control groups will include approximately 160 Alzheimer disease participants total (20 patients per facility). Demographic information obtained during the study preparation phase (mean age, gender, type of dementia by diagnosis, depression level, length of time in facility, date of onset of dementia, ethnicity) will be obtained to show that the facilities are comparable.

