6.1 Sample Size

As a pilot study, the planned sample size is not based on statistical power to detect specified effect sizes on intervention outcomes. Rather, the planned sample of 80 subjects per intervention group was selected in terms of pilot study feasibility. The planned sample is considered more than sufficiently adequate to address pilot trial questions related to feasibility (of study recruitment and conduct, delivery of intervention, data collection) and estimates of trial-related parameters, along with 95% confidence intervals (mean intervention effect size, variance in outcome measures in the study population, within-facility correlation in outcome measures, within-patient correlation in outcome measures). As pilot studies are well known to over-estimate intervention effect sizes and under-estimate measures of variance, it is crucial that confidence intervals (precision of the estimates) are also calculated and available for planning of larger studies.

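### Baseline arm tests ignore that whole facilities are assigned to arms, and the results help choose the covariates for the 12-week comparison

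*Combined protocol and SAP*

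**What the plan says.** Section 4.1 states: "At two facilities, the active light intervention will enlist staff to increase daylight exposure to Alzheimer residents". Section 4.2 states: "Patients at the other two facilities will receive usual care". The unit that receives a condition is therefore the facility. The documents describe no random allocation of facilities.

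Section 5.1 expects "approximately 160 Alzheimer disease participants total (20 patients per facility", and section 6.1 gives the split by arm: "the planned sample of 80 subjects per intervention group was selected in terms of pilot study feasibility".

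Section 6.0 opens with a general rule: "All analyses will include factors for facility and intervention (nested within facility". For baseline data it then names "analysis of variance for continuous data and chi-square methods for categorical data to compare the intervention groups". The results have a use: "If the intervention groups are found to differ on baseline levels of the outcome variables or other variables related to outcome", the variables concerned become adjusting covariates at 12 weeks. The 12-week model is an analysis of variance with "2-level factor for intervention, 8-level factor for facility, with intervention nested within facility".

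Section 6.0 states no significance level for the baseline tests, no error term for the arm comparison and no value for the within-facility correlation. That correlation is among the quantities the pilot is meant to estimate.

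**The concern.** Two statements in section 6.0 do not fit together. A facility factor is promised throughout, but an arm-by-category chi-square has no place for one. Each facility lies in a single arm, so stratifying by facility leaves no stratum in which the arms can be compared.

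If residents of one facility resemble each other, the variance of an arm difference is larger than the chi-square assumes, and the p-value is too small. The same holds for the ANOVA of continuous baselines if the arm is judged against variation between patients. Adding facility as a fixed factor and using the residual as the error term does not cure this, because the residual holds only within-facility variation.

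At stake are the comparability check, since section 5.1 collects demographics as evidence that the facilities are alike, and the adjustment set for the 12-week effect estimate, which section 6.0 wants for planning larger trials.

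**Working it through.** **Inputs from the documents.** Residents per facility m = 20 (section 5.1); 8 facilities (sections 3.0 and 6.0); 80 residents per arm (section 6.1).

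**Assumptions.** Two-sided 0.05 level; ICC from 0 to 0.20; four facilities per arm, from 80 / 20 = 4.

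**The plan's own figures.** 8 × 20 = 160 and 160 / 2 = 80, so both stated sample sizes reproduce. Two plus two facilities, as sections 4.1 and 4.2 read, would give 4 × 20 = 80 in total, which does not.

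**Error rate of a patient-level test.**
- Design effect: DE = 1 + (m − 1) × ICC = 1 + 19 × ICC.
- Actual two-sided error at nominal 0.05: 2 × [1 − Φ(1.96 / √DE)].
- Example at ICC 0.05: DE = 1 + 19 × 0.05 = 1.95; 1.96 / √1.95 = 1.404; error = 0.160.

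The formula was checked by beta-binomial simulation of the 2 × 2 chi-square (40,000 runs per setting, 4 + 4 facilities of 20, prevalence 0.15 to 0.7):

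| Assumed ICC | DE | Formula | Simulated, uncorrected | Simulated, continuity-corrected |
|---|---|---|---|---|
| 0 | 1.00 | 0.050 | 0.047–0.052 | 0.027–0.034 |
| 0.01 | 1.19 | 0.072 | 0.070–0.075 | 0.043–0.052 |
| 0.02 | 1.38 | 0.095 | 0.093–0.100 | 0.062–0.071 |
| 0.05 | 1.95 | 0.160 | 0.157–0.166 | 0.115–0.130 |
| 0.10 | 2.90 | 0.250 | 0.249–0.258 | 0.196–0.216 |
| 0.20 | 4.80 | 0.371 | not run | not run |

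**Continuous baselines** (20,000 runs, 4 + 4 facilities):
- Arm tested against patient-level error: 0.164 at ICC 0.05 and 0.257 at ICC 0.10.
- Facility as a fixed factor, residual error: 0.173 and 0.275.
- Arm tested against between-facility variation: 0.050 and 0.048.

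**Facility-level test for categorical data.** A t-test on the eight facility proportions has 8 − 2 = 6 df. Its simulated rate stays at about 0.046 to 0.053 for every ICC from 0 to 0.10.

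**Two plus two facilities.** The inflation depends mainly on m and so hardly changes: the uncorrected chi-square gives 0.163–0.177 at ICC 0.05. The facility-level test then has 4 − 2 = 2 df and a rate of about 0.046 to 0.055.

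**The case against.** The strongest reply is that the plan already declares facility a factor in all analyses, so the intent to allow for clustering is there. The intent stands, but section 6.0 does not say how a chi-square would honor it or which error term the ANOVA uses.

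A reader might infer that baseline differences will be flagged two to five times too often. The documents do not support that as a fact. They give neither an ICC nor a significance level, and the multiple needs an ICC of about 0.022 to 0.100. It is 1.4 at ICC 0.01 (0.072 / 0.05) and 7.4 at ICC 0.20 (0.371 / 0.05). With a continuity correction the rate at ICC 0.01 is about nominal.

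A reader might also infer that chi-square tests wrongly steer the 12-week model. That goes too far, for four reasons:
- Of the descriptors listed in section 6.0, gender and ethnicity are the evident categorical ones. They enter the model only if they are also related to outcome.
- The baseline outcome scores, the first trigger of the rule, go through ANOVA rather than chi-square.
- With no described randomization, a flag may show a real difference between facilities, and adjusting for a prognostic variable is not an error.
- The calculations cover baseline rejection rates only. No bias or loss of coverage at 12 weeks has been shown.

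Finally, this is a pilot that was not sized for power. That limits the weight of the point. It does not remove it, because the effect estimate and its interval are what the pilot passes on to later trials.

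**Conclusion.** The point holds as a flaw in method, with its size conditional on the ICC. The facility-factor promise and the chi-square choice are unreconciled. Patient-level baseline tests, categorical or continuous, are miscalibrated for facility-assigned arms. Without a continuity correction they flag too often at any positive ICC: about 0.07, 0.16 and 0.25 at ICC 0.01, 0.05 and 0.10, against a nominal 0.05. This rests on 20 residents per facility, an assumed two-sided 0.05 level, assumed ICCs, and a null of no systematic facility difference between arms.

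The consequence is limited to the comparability check and the way covariates are selected. Harm to the 12-week estimate is possible but not demonstrated. The change is worth making because it replaces a stated rule with a better one at little cost.

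**What to change.** In section 6.0:

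1. Drop the rule that baseline test results decide the covariates.
2. Always adjust each 12-week outcome for its own baseline value, which section 4.3 already collects, and for a short list of prognostic covariates named in advance.
3. Report baseline characteristics descriptively, by arm and by facility.
4. If any baseline arm test is kept, categorical or continuous, test the arm against between-facility variation, for example by a t-test on facility proportions or means. This has 6 df with four facilities per arm.
5. Reconcile the two plus two facilities of sections 4.1 and 4.2 with the eight of sections 3.0 and 6.0, because the df depend on it (2 df with two per arm).

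The cost is SAP wording and slightly more analysis work. Fewer baseline differences will be called significant, and a few degrees of freedom go to the prespecified covariates.

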4.3 Outcome Measures

The following outcome measures will be taken:

- 1. Patient outcomes will be completed at baseline and 12-weeks. For each of our major outcomes, we will use instruments that are well-validated for use in testing effects of short- to long-term interventions in AD:
 - a. Depression: Cornell Scale for Depression in Dementia (CSDD)
 - b. Neuropsychiatric Inventory Nursing Home Version (NPI-NH)
- 2. Trial conduct/methods outcomes:
 - a. Facility and staff support and participation: facilitators and obstacles.
 - b. Fidelity of light and control intervention: facilitators and obstacles.
 - c. Data collection fidelity: patient outcomes and light measures.
 - d. Estimates of subject recruitment, consent, and attrition rates: facilitators and obstacles.
 - e. Estimates (and confidence intervals) for study/trial planning: intervention effect size, variance of outcome measures, within-facility correlation in outcome measures, within-patient correlation in outcome measures (repeated measures).

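### Baseline scores enter the 12-week comparison only if the groups are found to differ; prespecified adjustment for each outcome's own baseline would usually give a more precise effect estimate

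*Combined protocol and SAP*

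**What the plan says.** Section 6.0 first compares the groups at baseline and "will utilize analysis of variance for continuous data and chi-square methods for categorical data to compare the intervention groups". The covariate rule that follows opens with a condition: "If the intervention groups are found to differ on baseline levels of the outcome variables or other variables related to outcome". Where the condition is met, the stated consequence is that "these variables will be included as adjusting covariates in the comparisons of 12-week outcomes". The default model has no baseline term: "12-week outcomes will be compared between intervention groups with analysis of variance (2-level factor for intervention, 8-level factor for facility"; the section describes intervention as nested within facility. It gives no test level, no size of difference and no unit of testing (patient or facility) that would count as differing.

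The data for adjustment will exist. Section 4.3 states: "Patient outcomes will be completed at baseline and 12-weeks". The outcomes listed there are the CSDD and the NPI-NH. Section 6.0 also plans to estimate the correlation between the two time points, but only as a separate planning figure; nothing else in the document brings baseline into the 12-week comparison.

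On purpose, section 6.1 says that "the planned sample of 80 subjects per intervention group was selected in terms of pilot study feasibility" and, of the planning estimates, that "it is crucial that confidence intervals (precision of the estimates) are also calculated and available for planning of larger studies".

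**The concern.** Whether adjustment helps depends on how well baseline predicts the 12-week score, and a baseline significance test does not measure that. When the arms are similar the test rarely fires, so a predictive covariate is usually discarded, and any gap too small to be detected passes into the estimated effect in proportion to the correlation. The covariate set is also fixed only after the data are seen, by an unstated criterion, and may differ between the CSDD and the NPI-NH.

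At stake is the intervention effect with its 95% interval, one of the estimates the pilot is meant to hand on to larger trials. The harm is lost precision and carried-over imbalance, not an invalid interval or an invalid pilot.

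**Working it through.** **Inputs from the documents.** Eight facilities (section 3.0, and the 8-level factor in 6.0), 20 patients per facility and about 160 in all (5.1), 80 per group (6.1). The planned sample reproduces: 8 × 20 = 160 = 2 × 80. It is a feasibility figure with no power calculation behind it. Sections 4.1 and 4.2 describe two plus two facilities; that layout is taken up in step 6.

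**Assumptions, because the documents give no values.** Two-sided 5% baseline test; ICC 0.05 (range 0.02 to 0.10); baseline to 12-week correlation 0.6 both within and between facilities (range 0.4 to 0.7); arms that differ at baseline by chance only; no true effect; results in units of the outcome SD. Since the unit of the baseline test is not stated, both a patient-level test and a facility-level test (6 df) were tried.

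**1. Standard errors in closed form.**
- Design effect: 1 + 19 × 0.05 = 1.95.
- Unadjusted: √(2/80 × 1.95) = 0.221.
- Adjusted, with equal correlation at both levels: 0.221 × √(1 − 0.6²) = 0.221 × 0.8 = 0.177.

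**2. How often the rule adjusts.**
- Patient-level test: it detects a gap above 1.975 × √(2/80) = 0.31. The test ignores clustering and the gap's true SD is 0.221, so this is 1.975/√1.95 = 1.41 standard errors, exceeded in about 16% of trials.
- Facility-level test: it detects a gap above 2.447 × 0.221 = 0.54, in about 5% of trials.

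**3. Imbalance left in.** A chance gap with SD 0.221 exceeds 0.2 in about 36.5% of trials and 0.3 in about 17.4%.
- Patient-level test: undetected gaps above 0.2 occur in about 36.5 − 16 ≈ 20% of trials, and above 0.3 in about 2% (simulated).
- Facility-level test: undetected gaps above 0.3 occur in about 17.4 − 4.9 ≈ 13%. The largest, about 0.54, would carry 0.6 × 0.54 = 0.32 into the group difference.

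**4. Simulation** (10,000 to 20,000 trials per setting). Unadjusted: facility-level comparison on 6 df. Adjusted: REML with random facility and one baseline slope.

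| Rule | Adjusts in | SD of estimate | Variance relative to always | Mean 95% half-width | Coverage |
|---|---|---|---|---|---|
| Always adjust | 100% | 0.177 | 1 | 0.426 | – |
| Conditional, patient-level test | 16.1% | 0.197 | 1.23 | 0.503 | 96.4% |
| Conditional, facility-level test | 4.9% | 0.212 | 1.43 | 0.516 | 95.8% |

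With no adjustment at all the simulated SD is 0.220, in line with step 1. Over the stated ranges the variance ratio runs from 1.04 to 1.5 (patient-level test) and 1.13 to 1.73 (facility-level test). With a 10% threshold the central values are 1.17 and 1.36.

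A second simulation with a different estimator (facility means, pooled within-facility slope, ICC 0.05) brackets these results:
- Correlation 0.5: (0.2053/0.1924)² = 1.14 and (0.2152/0.1924)² = 1.25.
- Correlation 0.7: (0.1882/0.1596)² = 1.39 and (0.2102/0.1596)² = 1.73.

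**5. Where the gain fails.** With within-facility correlation 0.6 and ICC 0.05, between-facility correlations of 0, 0.3 and 0.9 give ratios of 0.99, 1.07 and 1.49 (patient-level test) and 0.99, 1.15 and 1.92 (facility-level test). At ICC 0.10, within-facility correlation 0.7 and between-facility correlation 0, always adjusting loses: 0.96 and 0.88. Break-even is a between-facility correlation of about 0 at ICC 0.05 and about 0.2 at ICC 0.10.

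**6. Degrees of freedom and the smaller layout.** If the covariate is charged at facility level (5 df instead of 6), the adjusted half-width is 0.426 × 2.571/2.447 = 0.45, still below 0.50. With two plus two facilities of 20 or 40 patients, the variance ratios are 1.23 or 1.15 (patient-level test) and 1.46 or 1.48 (facility-level test). With 20 per facility, the half-width on 2 df falls from about 1.15–1.19 to 0.95.

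**The case against.** The strongest reply is that little turns on this in an unpowered pilot. Section 6.1 asks that intervals be calculated and available; it does not ask that they be as narrow as possible. The plan reports them, and their coverage is adequate. It also estimates the variances and correlations from which a planner could approximate the gain from adjustment. That reading of section 6.1 is fair. But the effect size with its interval is still a stated output, and a wider one than the data allow serves planning less well.

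Three further points stand as limits.

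- **The model.** The figures assume facility as a random effect nested within intervention, whereas section 6.0 nests intervention within facility. Each facility receives one condition, so a fixed 8-level facility factor would absorb the intervention effect. Adding baseline without repairing this would not deliver the gain.
- **The facility count.** With two plus two facilities, charging the slope at facility level takes 2 df to 1, and the interval would become about 0.8 × 12.71/4.30 = 2.4 times the unadjusted width. This is a worst case that a slope estimated across patients need not incur, but the method has to be stated.
- **Chance imbalance.** No random allocation is described. With systematic differences between facilities the trigger rates and undetected-gap rates above do not transfer, because larger gaps would trigger adjustment more often. This limits the figures rather than the advice: adjustment for measured baseline differences is then more useful, though it cannot remove unmeasured ones.

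**Conclusion.** The point holds and should be fixed. Under the central assumptions the conditional rule has about 1.2 times (patient-level test) or 1.4 times (facility-level test) the variance of always adjusting. That is a loss of 1 − 1/1.23 = 19% or 1 − 1/1.43 = 30% of the information on the effect.

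Confidence is medium, because the test level, the ICC and both correlations are assumed, and the result depends mainly on a between-facility correlation that nobody yet knows. Usually is therefore the right word. Adjustment does not overcome the small number of facilities, which governs the width of the interval under any rule.

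**What to change.** Replace the conditional sentence in section 6.0 with wording such as:

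> Each 12-week outcome will be analysed with the baseline value of the same outcome as a prespecified covariate in all cases, in a model that treats facility as the unit of allocation (random facility nested within intervention).

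In addition:
- Keep the baseline comparisons descriptive and do not use them to choose covariates.
- Name any further covariate in advance, or report it as a sensitivity analysis.
- Report the unadjusted difference alongside, since the gain depends on a between-facility correlation not yet known.
- State how degrees of freedom will be counted, and reconcile the number of facilities in sections 3.0, 4.1, 4.2 and 6.0.

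The cost is SAP wording and one covariate degree of freedom; no new data are needed. The sentence also corrects the nesting, which section 6.0 needs in any case. A small loss of precision is possible if facility-level baseline and outcome prove unrelated.

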3.0 STUDY DESIGN

The research will be conducted as a 12-week field study in eight Silverado dementia care facilities in Los Angeles and Orange County. Silverado is an assisted living service provider that delivers care for those with Alzheimer, dementia and other memory-impairing diseases. Data collection will occur twice during the study: baseline measures at the beginning of the study and outcome measures at the end of the study.

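### The outcome model in Section 6.0 reverses the nesting and names no error term, so it does not determine a valid intervention effect or confidence interval

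*Combined protocol and SAP*

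**What the plan says.** Section 6.0 sets one rule for every analysis: "All analyses will include factors for facility and intervention (nested within facility"). It repeats the rule for the 12-week comparison, an analysis of variance with a "2-level factor for intervention, 8-level factor for facility, with intervention nested within facility". It does not say whether facility is fixed or random, which mean square is the error term, or how many denominator df apply. Baseline comparisons use analysis of variance for continuous variables and "chi-square methods for categorical data to compare the intervention groups". Baseline differences then decide which covariates enter the outcome model.

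Condition is assigned to whole facilities. Section 4.1: "At two facilities, the active light intervention will enlist staff to increase daylight exposure to Alzheimer residents". Section 4.2: "Patients at the other two facilities will receive usual care". Those two sections describe two plus two facilities, whereas Section 3.0 describes a "12-week field study in eight Silverado dementia care facilities" and Section 6.0 uses eight levels.

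For planning larger trials, Section 6.0 asks for the effect size, the variance across patients and across facilities, and the within-facility correlation, each with a 95% CI. Section 6.1 says "it is crucial that confidence intervals (precision of the estimates) are also calculated and available for planning of larger studies".

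**The concern.** A factor is nested within facility only if its levels vary inside a facility. Here they do not: every resident of a facility gets the same condition. The result therefore depends on how the analyst reads the sentence.

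- **Reading A, literal:** facility is fixed and entered first. Intervention is then fully determined by facility, and nothing is left to estimate.
- **Reading B:** intervention is entered first, facility within intervention second, and both are tested against the patient residual. An effect is estimated, but its standard error leaves out facility-to-facility variation.
- **Reading C:** facility is random within intervention. This is valid, but no section says it.

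Two further outputs are exposed. If the between-facility variance is taken from the 7-df facility term of Reading A, it and the ICC absorb any difference between arms. The baseline chi-square comparisons name no allowance for clustering.

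The effect estimate, its CI and the within-facility correlation are what this pilot is to hand to a larger trial. A CI that is too narrow would mislead that planning.

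**Working it through.** **Inputs.** Eight facilities (Sections 3.0 and 6.0); 20 patients per facility and about 160 in total (Section 5.1); 80 per group (Section 6.1). These agree: 8 × 20 = 160, and 80 / 20 = 4 facilities per arm. Two plus two facilities give 4 × 20 = 80, which does not match 160. The documents state no ICC, test level or denominator df. Assumed: ICC from 0 to 0.10, two-sided 5%, total SD of 1.

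**Degrees of freedom.** The design matrix has rank 8 with facility alone and rank 8 with facility plus intervention, so intervention adds 8 − 8 = 0 df (Reading A). Entered first, intervention has 1 df, facility within intervention 6 and residual 160 − 8 = 152.

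**Reading B, type I error.** The ratio of the intervention mean square to the residual mean square is inflated by k = 1 + 20·ICC/(1 − ICC). The true error rate is P(F(1,152) > 3.903/k). At ICC 0.05, k = 1 + 1/0.95 = 2.053 and 3.903/2.053 = 1.90, which gives 0.170.

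**CI half-widths, in SD.**
- Patient residual: t(152) × √(4(1 − ICC)/160), with t = 1.976. At ICC 0.05: 1.976 × √0.02375 = 0.304.
- Facility within intervention: t(6) × √(2(ICC + (1 − ICC)/20)/4), with t = 2.447. At ICC 0.05: 2.447 × √0.04875 = 0.540.

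| Assumed ICC | Type I error, Reading B | Coverage of nominal 95% CI | Half-width, Reading B | Half-width, 6 df |
|---|---|---|---|---|
| 0 | 5.0% | 95% | 0.31 | 0.39 |
| 0.01 | 7.4% | 93% | 0.31 | 0.42 |
| 0.05 | 17.0% | 83% | 0.30 | 0.54 |
| 0.10 | 27.3% | 73% | 0.30 | 0.66 |

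Simulation (40,000 trials per ICC) gave 5.1%, 7.3%, 16.9% and 27.4% for Reading B, and 5.0%, 4.8%, 5.0% and 5.1% with the facility-within-intervention error term.

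**If there are only four facilities of 20.** The correct denominator has 2 df (t = 4.303). At ICC 0.05 the half-width is 4.303 × √(2(0.05 + 0.0475)/2) = 1.34 SD, against 0.43 SD from the patient residual (76 df).

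**ICC from the 7-df facility term.** With a true ICC of 0.05 and an arm difference of d SD, the expected between-facility variance is 0.05 + 8(d/2)²/7.
- d = 0.2: 0.0614; ICC = 0.0614/(0.0614 + 0.95) = 0.061; design effect 1 + 19 × 0.061 ≈ 2.15.
- d = 0.5: 0.1214; ICC = 0.113; design effect 3.15.

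The true design effect is 1 + 19 × 0.05 = 1.95. This bias does not arise in Reading B, and the plan does not say how the ICC is to be estimated.

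**Unadjusted chi-square at baseline.** Simulated with 80 against 80, beta-binomial data and an assumed prevalence of 30%, false positives are 5.0%, 7.6%, 16.9% and 25.6% at ICC 0, 0.01, 0.05 and 0.10.

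**The case against.** The strongest reply is that the plan never chooses Reading B. It puts facility in every model and asks for variance across facilities and a within-facility correlation. These are variance components and suggest that facility was thought of as random; the nesting may simply be written the wrong way round. Reading A would also expose itself, because the software would return no intervention effect. This is fair, and all the inflation figures are conditional on Reading B and an assumed ICC. But planning to estimate an ICC does not commit the plan to using it in the CI for the effect. A fixed facility factor removes facility variance from the residual, so under Reading B it makes the interval narrower.

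Second, the rule for all analyses could be held to cover the chi-square tests. A facility factor cannot supply that allowance, because intervention is constant within facility. The 30% prevalence remains an assumption.

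Third, four sections (3.0, 5.1, 6.0 and 6.1) fit eight facilities, so the four-facility figures are the less likely case. That is right: they show why the count must be settled and are not the main result.

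Fourth, this is a pilot without a power calculation, and its feasibility outcomes are unaffected. That lowers the weight of the p-value but not of the CI, on which Section 6.1 insists.

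**Conclusion.** The concern holds. The model sentence contradicts the design in Sections 4.1 and 4.2 and, run as written, cannot produce the intervention effect. One natural repair gives an interval that is too narrow whenever the ICC is above zero: at an assumed ICC of 0.05, about 0.30 SD where 0.54 SD is correct, with 83% coverage. These sizes assume eight equal facilities of 20 and no facility allowance in the standard error. The 0-df result needs neither an ICC nor the facility count; it follows from each facility having one condition. The ICC and chi-square figures are secondary and conditional on methods the plan leaves open. This must be fixed before analysis.

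**What to change.** Replace the model sentence in Section 6.0 with: *Intervention is a fixed factor and facility is a random factor nested within intervention. The intervention effect and its 95% CI use the facility-within-intervention mean square, with number of facilities minus 2 df (6 for eight).* Correct the general rule at the start of the section in the same way. Then:

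- For unequal facility sizes or patient-level covariates, use a linear mixed model with small-sample df, or compare covariate-adjusted facility means.
- State that df stay at facilities minus 2 even if the facility variance is estimated as zero, and that this overrides any software default. With eight facilities a negative variance estimate has a 45% chance at ICC 0.01 and 18% at 0.05.
- Estimate the between-facility variance and ICC with intervention in the model, and name the method for their CIs.
- Use the same error term for continuous baseline variables. For categorical ones, replace plain chi-square with a cluster-adjusted method, such as a t-test on facility proportions.
- Reconcile the eight facilities of Sections 3.0 and 6.0 with the two plus two of Sections 4.1 and 4.2, and state the resulting df.

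The cost is SAP wording; no new data are needed. The price is a wider CI, even if the true ICC is zero (half-width 0.39 against 0.31 SD).
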